12. INFORMED CONSENT

Waiver of Documented Consent for Aiding in Determining Preliminary Eligibility during Research Recruitment:

We are asking for a waiver of documented consent while recruiting subjects to appropriately identify potential subjects during the phone screening procedure. The phone screen is considered no more than low risk to the potential subjects, since we will not perform any procedure, and the probability and magnitude of harm or discomfort anticipated in this research are not greater than those ordinarily encountered in daily life. In addition, our methods of recruitment do not allow the pre-screener to directly contact or call the patient unless the patient, themselves, contacts the study team first through contact information provided on study advertisements or the patient's treating physician refers them to the study.

The information inquired about and collected from the phone screen is necessary to ascertain the potential subject's suitability for entry into the study. While reviewing responses and information during the phone screen, the screener may determine that the potential subject qualifies for the study and then proceed to ask if they would be interested in participating. The screener will indicate to potential subjects that review of their medical records will be involved in determining formal study eligibility.

If a subject qualifies for the study, information collected from the phone screens will be entered into two separate password-protected databases: one for personal identifiable information, and one containing the participant's responses. In the second database, the subject will be identified with a recruitment number that is determined simply by the order in which subjects contact us. This second database, linking participants' personal identities to code numbers will be stored in locked research files separately from research records. Thus, the hard copy Phone Screen will be shredded immediately for subjects who do not qualify, and after the information has been entered into our password-protected databases for subjects who do qualify (after written consent is obtained). The Phone Screen (excluding the page with contact information) will be labeled with the recruitment number, which will also be used to link the two databases. Hard copies of screening responses will be labeled only with the date and the participant recruitment number.

Consenting Procedures:

Once a potential study participant expresses interest in our study and meets preliminary eligibility requirements, as determined by phone screening, the subject will be asked to digitally provide consent via REDCap, using an IRB-approved consent form, approximately one week before their first study session. The consent process will take place prior to performing any study related procedures. While participants have the consent form open in REDCap, a study team member will call participants by phone or video to describe the study, including detailed information about risks and benefits, and answer questions. The study team member will provide potential subjects with an IRB-approved consent form in REDCap. Potential subjects will be given ample time to read this consent form or may request to read it at another time. Potential study subjects will be given the opportunity to ask and receive answers to all questions they may have about the study, its risks and benefits, or the consent form itself before digitally signing the consent form. As this research is subject to HIPAA privacy rule provisions, subjects will also be requested to digitally sign a separate HIPAA authorization in REDCap for the use of protected health information. Participants will have the opportunity to download a signed copy of the consent and HIPPA authorization forms for their records.

Over phone or video, questions will be asked and elicited in order to ascertain that participants comprehend the study procedures as well as potential risks involved, prior to consenting to the study. All study related questions from study participants that a research staff member is unable to address will be referred to the Principal Investigator, or other co-investigators. No clinical information beyond screening (extended phone screen and clinical information) will be gathered until participants have provided written, signed informed consent.

Potential subjects who fulfill the eligibility criteria will be offered further participation in this study. Only subjects who have consented and provided HIPAA authorization will have identifiers or linked information (e.g., subjects initials, study numbers, etc.) recorded on the Screening/Enrollment Log.

All digitally signed consents will be maintained in REDCap and on laboratory password protected computers and servers, as well as in marked binders secured in locked filing cabinets within private offices at [name] and [name]'s Laboratory at the ACTRI. Documentation of this process will be written form and placed in the research record. A copy has been uploaded for IRB review and approval.

13. ALTERNATIVES TO STUDY PARTICIPATION

The alternative to participation in this study is not to participate.

14. POTENTIAL RISKS

This study may involve some risk, although the risks are considered minimal.

Risks of Psychological and Cognitive Assessments:

The main risks are that clinical interviews, cognitive testing and self-report questionnaires are time-consuming. Material elicited during interviews may be upsetting to some study participants. Others may find cognitive tasks to be challenging or frustrating. These assessments, however, rarely pose psychological risks for study

participants.

Risks and discomforts associated with heat pain stimuli:

Reddening/darkening of the skin may occur with thermal stimulation; this is transient and disappears after termination of the testing. The heat stimuli, which are of moderate to strong intensity, will not damage the skin. Heat pain stimulation has been used extensively without any long-term adverse effects and do not cause permanent tissue damage [29-31].

Risks and discomforts associated with cold water bath task:

The cold water bath is a commonly used pain task and is considered safe [39]. However, it is possible (although rare) that a participant might react to immersing their hand in the cold water with a stress response, that is, increased heart rate and/or, in extreme instances, fainting. It is also possible that discomfort and numbness of the hand may occur during and after submerging it into the cold water bath. This is temporary and will not damage the skin..

Risks and discomforts associated with brushing and compression stimuli:

There are no known risks of the gentle brushing. Pressure stimuli may be uncomfortable to some participants, but the pressure will be lower than a standard blood pressure cuff and thus familiar to all participants. Repeated compression could theoretically dislodge any active blood clots in the participant's limb.

Risks for screening and questionnaires:

We have included a number of validated questionnaires to assess variations across individuals. Some of these items include sensitive questions about one's psychological and health state.

Risks of MRI and fMRI:

People are at risk for injury from the MRI magnet if they have pacemakers or other implanted electrical devices, brain stimulators, some types of dental implants, aneurysm clips (metal clips on the wall of a large artery), metallic prostheses (including metal pins and rods, heart valves, and cochlear implants), permanent eyeliner, implanted delivery pump, or shrapnel fragments. Welders and metal workers are also at risk for injury because of possible small metal fragments in the eye of which they may be unaware.

It is not known if MRI is completely safe for a developing fetus. Therefore, all women of childbearing potential will have a pregnancy test performed no more than 24 hours before each MRI scan. The scan will not be done if the pregnancy test is positive.

People with fear of confined spaces (i.e. claustrophobia) may become anxious during an MRI. Those with back problems may have back pain or discomfort from lying in the scanner. The noise from the scanner is loud enough to damage hearing, especially in people who already have hearing loss. There are no known long-term risks of MRI scans.

Risk of Breach of Confidentiality:

There is a risk that information collected in our study could become known to individuals not involved in our study. MRI data are not used for diagnostic purposes and all data are associated only with identification numbers. Breaches in confidentiality could impact future insurability or employability. However, in our experience, this has not occurred with this type of research.

15. RISK MANAGEMENT PROCEDURES AND ADEQUACY OF RESOURCES

Privacy of participants:

Research staff will be trained by the PI to respect the privacy and confidentiality of NIH employees and staff, especially with regard to sensitive, private information. All data will be de-identified and personnel will not view data alongside identifying information, which will reduce the possibility that lab personnel would be able to associate sensitive information with individuals. The lab will discuss professionalism and confidentiality, and if

lab personnel are acquainted with any potential participants, a different investigator will interact with that participant.

Confidentiality of Data:

We will actively protect confidentiality of the subjects and the data at each step. All medical records and subject data will be kept confidential and will only be reviewed by the participating investigators. Data will be de-identified and stored using codes that we assign. De-identified data will be kept on password-protected computers or in locked cabinets at UC San Diego. Only study investigators will have access to the data.

Psychological risks:

Participants will be informed that they can skip any questions they do not wish to answer, and that participation is voluntary. If participants are triggered by items on study questionnaires, they will be offered a break to disengage from the task and asked whether they wish to continue or not. If participants remain upset referrals to psychological care at UC San Diego will be made.

MRI:

Subjects will be screened for the conditions described in the “Risks of MRI and fMRI” section before having any scan, and if they have any, they will not receive an MRI scan. In addition, all magnetic objects (for example, watches, coins, jewelry, and credit cards) must be removed before entering the MRI scan room. Subjects will be fitted with hearing protection. Subjects will be instructed to let us know right away should the hearing protection come loose during the scan. Subjects will also be instructed to notify the investigators if they have hearing or ear problems. Subjects will be asked to complete an MRI screening before having the MRI.

Sensory stimuli:

Sensory testing procedures and risks will be described carefully and participants will be encouraged to provide immediate feedback if a stimulus is not tolerable. All participants will be screened to ensure they do not have any history of blood clots of first degree family members with clotting disorders.

All risks to subjects are minimal and unlikely to have significant impact. If subjects are injured by study procedures they will be evaluated by the study physician will be treated by care providers at UC San Diego. Incidental findings such as from MRI will be shared with the subject by a medical provider affiliated with the study and appropriate referrals for follow-up care will be made.

Cold water bath:

Participants will be instructed and reminded that they can remove their hand from the cold water in the event they find it intolerable or do not wish to continue.

Monitoring:

An Independent Monitor (IM) will monitor the activities of this study for purposes of evaluating participant safety and study integrity. The study PI will oversee all experimental procedures of the proposed research activities. In the event of an adverse safety event, protocol deviations and adverse events will be promptly (less than 24 hours) reported to the IMC and the IRB.

This study will follow the Data and Safety Monitoring Plan submitted to NCCIH for the proposed R00 award:

Adverse Event (AE):

An adverse event (AE) is any untoward medical occurrence in a subject during participation in the clinical study or with use of the experimental agent being studied. An adverse finding can include a sign, symptom, abnormal assessment (laboratory test value, vital signs, electrocardiogram finding, etc.), or any combination of these regardless of relationship to participation in the study.

Unanticipated Problems (UP):

The Office for Human Research Protections (OHRP) considers unanticipated problems involving risks to subjects or others to include, in general, any incident, experience, or outcome that meets **all** of the following criteria:

- Unexpected in terms of nature, severity, or frequency given (a) the research procedures that are described in the protocol-related documents, such as the IRB-approved research protocol and informed consent document; and (b) the characteristics of the subject population being studied;
- Related or possibly related to participation in the research (“possibly related” means there is a reasonable possibility that the incident, experience, or outcome may have been caused by the procedures involved in the research); and
- Suggests that the research places subjects or others at a greater risk of harm (including physical, psychological, economic, or social harm) than was previously known or recognized.

Serious Adverse Event (SAE):

A serious adverse event (SAE) is one that meets one or more of the following criteria:

- Results in death
- Is life-threatening (places the subject at immediate risk of death from the event as it occurred)
- Results in inpatient hospitalization or prolongation of existing hospitalization
- Results in a persistent or significant disability or incapacity
- Results in a congenital anomaly or birth defect

An important medical event that may not result in death, be life threatening, or require hospitalization may be considered an SAE when, based upon appropriate medical judgment, the event may jeopardize the subject and may require medical or surgical intervention to prevent one of the outcomes listed in this definition.

Time Period and Frequency for Event Assessment and Follow-Up:

Unanticipated problems will be recorded in the data collection system throughout the study.

The PI will record all reportable events occurring during the testing session or reported by the participant to the PI within 30 days of the testing session. If participating in multiple study session, at each study visit, the investigator will inquire about the occurrence of AE/SAEs since the last visit. Events will be followed for outcome information until resolution or stabilization.

Characteristics of an Adverse Event Relationship to Study Intervention:

To assess relationship of an event to study intervention, the following guidelines are used:

1. Related (Possible, Probable, Definite)
 - a. The event is known to occur with the study intervention.
 - b. There is a temporal relationship between the intervention and event onset.
 - c. The event abates when the intervention is discontinued.
 - d. The event reappears upon a re-challenge with the intervention.
2. Not Related (Unlikely, Not Related)
 - a. There is no temporal relationship between the intervention and event onset.
 - b. An alternate etiology has been established.

Expectedness of SAEs:

The Study PI and Independent Monitoring Committee will be responsible for determining whether an SAE is expected or unexpected. An adverse event will be considered unexpected if the nature, severity, or frequency of the event is not consistent with the risk information previously described for the intervention.

Severity of Event:

The following scale will be used to grade adverse events:

1. Mild: no intervention required; no impact on activities of daily living (ADL)
2. Moderate: minimal, local, or non-invasive intervention indicated; moderate impact on ADL

3. Severe: significant symptoms requiring invasive intervention; subject seeks medical attention, needs major assistance with ADL

Unanticipated Problem Reporting:

Incidents or events that meet the OHRP criteria for unanticipated problems require the creation and completion of an unanticipated problem report form. OHRP recommends that investigators include the following information when reporting an adverse event, or any other incident, experience, or outcome as an unanticipated problem to the IRB:

- Appropriate identifying information for the research protocol, such as the title, investigator's name, and the IRB project number;
- A detailed description of the adverse event, incident, experience, or outcome;
- An explanation of the basis for determining that the adverse event, incident, experience, or outcome represents an unanticipated problem;
- A description of any changes to the protocol or other corrective actions that have been taken or are proposed in response to the unanticipated problem.

To satisfy the requirement for prompt reporting, unanticipated problems will be reported using the following timeline:

- Unanticipated problems that are serious adverse events will be reported to the IRB, Independent Safety Monitor(s), and NCCIH within 7 days of the investigator becoming aware of the event.
- Any other unanticipated problem will be reported to the IRB, Independent Safety Monitor(s), and NCCIH within 14 days of the investigator becoming aware of the problem.

Adverse Event Reporting of Non-IND Studies:

SAEs that are unanticipated, serious, and possibly related to the study intervention will be reported to the Independent Safety Monitor(s), IRB, and NCCIH in accordance with requirements.

- Unexpected fatal or life-threatening AEs related to the intervention will be reported to the NCCIH Program Officer, and Independent Safety Monitor(s) within 3 days of the investigator becoming aware of the event. Other serious and unexpected AEs related to the intervention will be reported within 7 days.
- Anticipated or unrelated SAEs will be handled in a less urgent manner but will be reported to the Independent Safety Monitor(s), IRB, and other oversight organizations in accordance with their requirements. and will be reported to NCCIH on an annual basis.
- All other AEs documented during the course of the trial will be reported to NCCIH on an annual basis by way of inclusion in the annual report and in the annual AE summary which will be provided to NCCIH and to the Independent Monitors. The Independent Safety Monitor(s) Report will state that all AEs have been reviewed.

Halting Rules:

The study will be halted Halt if any SAE related to study participation or two severe AEs/reactions occur, until a complete safety review is convened.

Measurement and Reporting of Subject Accrual:

Review of the rate of subject accrual will occur monthly during the recruitment phase to ensure that a sufficient number of participants are being enrolled, in keeping with proposed recruitment projections, and that they meet eligibility criteria and fulfill the targeted ethnic diversity goals outlined in the grant proposal.

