Participants will be fitted with a BioNomadix RSP respiratory transducer belt and amplifier. Respiration rate will be recorded with MP160 and digitized using AcqKnowledge at rest and throughout the entire session.

We will test the analgesic effects of light slow brushing, deep pressure, and neutral touch (tapping) on induced pain using a modified affective-CPM paradigm. In this session, we will test the effect of non-painful touch stimuli on the conditioned pain stimulus, as has been conducted by [6, 7]. Both segmental (same dermatome) and nonsegmental (different dermatome) effects will be tested in order to determine whether pain inhibition is a bottom-up neural effect or an indirect affective effect.

After identifying limb locations identified as most comfortable by patients, we will perform calibration and will administer six affective-CPM blocks in an order counterbalanced across subjects: brushing, pressure, and

tapping, repeated with testing within a segment (same dermatome) and outside a segment (different dermatome).

Calibration (psychophysical testing): Session 2 calibration will be confirmed by testing the temperature rated as a 6 in Session 1 and adjusting as necessary.

Each affective-CPM block will include: phasic heat pain (baseline), heat pain with concurrent touch stimulus (test), and then test phasic heat perception once again (post-test), as follows:

Baseline: Heat will be administered using a thermode for 30s. Pain intensity ratings for the heat will be collected every 10s for a total of 3 ratings.

Test: 0-30s: rate pleasantness and intensity of the touch stimulus (brushing, pressure, or tapping). 30-60s: administer heat pain using a thermode concurrently; pain intensity rating of heat pain given every 10sec for a total of 3 ratings

Post-test: Repeat of baseline.

Between blocks the participant will rest for approximately 10-15min until sensation has dissipated to avoid habituation to test stimuli.

Session 2 will occur at the ACTRI and will take approximately 1-2 hours to complete.

Session 3: MRI Session for healthy controls (optional, offered until $N = 20$ controls have completed MRI)

A urine pregnancy (if applicable) test will be performed.

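### The halting rule ends a safety halt when the review is convened, so on its wording testing could resume before the review reaches a conclusion

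*Combined protocol and SAP*

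**What the plan says.** The halting rule is a single sentence in section 15 of the combined protocol and SAP, under Halting Rules. The study stops "if any SAE related to study participation or two severe AEs/reactions occur, until a complete safety review is convened". There are two triggers (one related SAE, or two severe events or reactions) and one end point, the convening of a review.

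The rest of section 15 supplies the surrounding safety machinery:

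- Monitoring gives an Independent Monitor a general safety and integrity role and says that "adverse events will be promptly (less than 24 hours) reported to the IMC and the IRB". It then states: "This study will follow the Data and Safety Monitoring Plan submitted to NCCIH for the proposed R00 award".
- Expectedness of SAEs says: "The Study PI and Independent Monitoring Committee will be responsible for determining whether an SAE is expected or unexpected".
- Unanticipated Problem Reporting allows 7 days for problems that are SAEs. For the rest: "Any other unanticipated problem will be reported to the IRB, Independent Safety Monitor(s), and NCCIH within 14 days".
- Adverse Event Reporting of Non-IND Studies sets 3- and 7-day limits for unexpected related events and annual reporting for the remainder. It adds: "The Independent Safety Monitor(s) Report will state that all AEs have been reviewed".

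**The concern.** A halt exists so that a safety question is answered before the next participant is exposed. The triggers here are not trivial. By the protocol's own definitions an SAE includes death, a life-threatening event, hospitalization or lasting disability, and a severe event is one with significant symptoms that needs invasive treatment, medical attention or major help with daily activities. If the halt lapses when the review is called together, a justified stop can end with the question still open, and heat and cold testing can restart while the reviewers are still deliberating.

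What is at stake is whether the rule, applied by someone reading it as written, does the job it was put there to do. No estimate, error rate or comparison depends on it.

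**Working it through.** The point is textual. There is no stated figure to reproduce and no arithmetic to run. The check has two steps: parse the rule, then look for any other text that closes the gap.

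**Step 1: the sentence.** The word *until* marks the end of the halt. The event attached to it is that the review *is convened*. The adjective *complete* describes the kind of review to be called. It does not say that the review has been finished. As worded, the halt therefore ends at the start of a full review.

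**Step 2: the neighbouring text.** Each part of section 15 that bears on safety events was set against one question: does it make restart depend on the review's completion or result?

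| Section 15 text | What it governs | Sets a restart condition? |
|---|---|---|
| Monitoring: Independent Monitor | General oversight of safety and integrity | No |
| Monitoring: under-24-hour reports | Notice to the IMC and IRB | No |
| Sensory stimuli: injured subjects | Evaluation and care of the individual | No |
| Expectedness of SAEs | Classifying an SAE as expected or unexpected | No |
| Unanticipated Problem Reporting: 7 and 14 days | Notice to the IRB, monitor(s) and NCCIH, and report content | No |
| Adverse Event Reporting: 3 and 7 days, annual | Notice to the NCCIH Program Officer, monitor(s) and others | No |
| Monitor's report on AEs | Statement that AEs were reviewed | No |
| Halting Rules | Triggers and end of the halt | Only that a review is convened |

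The other available sections contain no restart condition either. So the available text leaves three things unstated: that the review must conclude, that its conclusion must support resumption, and who takes part in it.

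**Limits of the check.** Section 21 was not available to read. Section 11 refers to it for the list of team members, so it is an unlikely place for a restart rule. The Monitoring text presents section 15 as following the plan submitted to the funder. Whether it reproduces that plan in full cannot be checked from these documents.

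**The case against.** The strongest reply is that this is a drafting slip and not a decision. The sentence is visibly garbled, with a repeated verb. If an unfinished review were enough to lift the halt, the word *complete* would do little work. The natural intention is that the study stays stopped until a full review has taken place. That is very likely right, and it is why the point is minor. It also favours the edit, since the rule would then say what was meant.

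The second reply is that other duties make a silent restart unlikely. Events go to the IMC and IRB in under 24 hours, and unanticipated-problem reports are expected to describe corrective actions. This lowers the practical risk. It does not supply the missing condition, because these are duties to notify and describe, not permission to resume.

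Three stronger readings are tempting, and the documents support none of them.

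- A reader might infer that the authors chose *convened* deliberately, because the monitor's report is described in completed terms ("The Independent Safety Monitor(s) Report will state that all AEs have been reviewed"). That statement belongs to the bullet on remaining AEs and annual summaries. It says little about what the halting sentence was meant to say.
- A reader might measure the harm by the heat and cold a participant would receive in a session resumed too early. That is the ordinary planned exposure, the same under either wording, so it is not excess harm.
- A reader might infer that the under-24-hour report already covers every other reporting limit. It does not. That report goes to the IMC and IRB, while the 3-, 7- and 14-day limits also involve NCCIH or its Program Officer.

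**Conclusion.** The concern holds as a minor participant-safety correction. On its wording the halting rule allows testing to resume once a review has been called together, and nothing else in the available text ties restart to the review's outcome. The wording was probably meant to require a completed review.

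The size cannot be put in numbers. The documents give neither a probability of a trigger nor the time from convening a review to its conclusion. Section 14 describes the risks as minimal, and the point has no practical effect unless a trigger occurs. Endpoints, sample size and analysis are untouched, and the two triggers are not in question.

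The conclusion assumes that *convened* carries its ordinary meaning and that no restart condition sits in text that was not available, such as a fuller version of the monitoring plan. If that plan already requires a concluded review, the remaining task is only to bring this sentence into line with it.

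**What to change.** Replace the Halting Rules sentence with the following. The words in quotation marks are retained from the current text.

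> The study will be halted "if any SAE related to study participation or two severe AEs/reactions occur", and no testing session will take place until a complete safety review, including the Independent Monitor, has been completed and has concluded that the study may resume.

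This keeps both triggers, removes the stray repeated verb, and moves the end of the halt from the start of the review to a favourable conclusion. Naming the Independent Monitor is the one addition, because the current text does not say who takes part. Section 15 uses several labels for the oversight body (Independent Monitor, IMC, Independent Safety Monitor(s), Independent Monitoring Committee), so the sponsor should confirm which is meant here.

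No reporting clause needs to be added. The duties under Monitoring, Unanticipated Problem Reporting and Adverse Event Reporting, including notice to NCCIH, stay as they stand.

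The cost is one sentence submitted to the IRB, with no extra participants or procedures. The small downside is that a triggered halt will last until the review concludes, which may delay some sessions.
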